8.0 Data and Specimen Long Term Storage and Use

22-432 Effects of narratives on demand for low and high ventilated cigarettes and substitution for alternative products.

8.1 If you will store data or specimens for future use, describe where you will store the data or specimens, how long they will be stored, and how and by whom the data or specimens will be accessed:

All participant data, including electronic data, will be stored in secure places to protect confidential participant information. Secured places will include locked filing cabinets, locked rooms accessible only to study personnel, and/or password-protected databases. Moreover, all data will be quality controlled in preparation for data analyses. All discrepancies in data entry will be checked against the raw data source, and the correct data entry will be used. All data entered into spreadsheets and databases will be coded by participant ID number and not by name (i.e., first and last name). Additionally, all entered data will be backed up on secure password-protected servers. Computers used in the studies will also be password protected, accessible only by study personnel. IRB regulations will be strictly adhered to in the conduct of the proposed research. Specifically, prior to implementation of any protocol changes, amendments will be submitted to the IRB for approval.

8.2 For specimens, list the data to be stored or associated with each specimen:

N/A

8.3 Describe the procedures to release data or specimens outside of the research team, including the process to request a release, approvals required for release, who can obtain data or specimens, and what data will be provided with specimens:

Investigators will adhere to all NIH requirements regarding data sharing. Participant data collected in this project will be de-identified before sharing for analysis outside of the study team. As part of this process, all investigators will be required to agree to the following conditions: 1) will adhere to the reporting responsibilities; 2) will not redistribute the data beyond the requesting individual and named collaborators; 3) will give appropriate acknowledgement; 4) will not use the data for commercial purposes; and 5) will obtain appropriate ethical approvals.

Results from research conducted will be shared and disseminated, including: regular project meetings, annual meetings, symposia, workshops, and/or conferences for related groups. Manuscripts will be written and submitted for publication in peer-reviewed journals/conferences, following the NIH Public Access Policy guidelines. All necessary ethical approvals will be obtained.

22-432 Effects of narratives on demand for low and high ventilated cigarettes and substitution for alternative products.

Data requests will be reviewed by the principal investigator and data will be shared with the expectation of acknowledgment of funding source and primary study team.

8.4 Describe the identifiers to be included with stored data or specimens, as well as any key or code that could be used to make them identifiable. Describe where the code will be stored, who will have access to it, and when it will be destroyed:

Original signed consent forms and other forms with identifying information will be stored in a study specific binder for this protocol, separate from all other study documents with participant ID.

All screened participants are assigned study IDs that are thereafter associated with all collected data, whether paper or electronic. The electronic de-identified data is stored on the shared servers which are password protected. Non-electronic data that is collected is stored in study-specific binders identified only by study ID. These binders are stored in a locked room within ARRC.

Study ID and full name are available together electronically only in REDCap [1], a widely used secure web-based application that enables us to build and maintain a participant database. Specifically, we use REDCap to collect demographic and other screening criteria for eligibility for study enrollment. This service is password protected and has been approved by Virginia Tech IRB.

8.5 Please select the identifiers you will obtain (whether directly from participants or from another source), including but not limited to:

	Name
	Geographical subdivisions smaller than a state, including street address, city, county, precinct, zip code, and equivalent geocodes (note, the initial three digits of a zip code are not considered identifiable)
	Elements of dates (except year) for dates directly related to an individual, including birth date, admission date, discharge date, date of death, and single year of age over 89 and all elements of dates (including year) indicative of such age (note, such ages and elements may be aggregated into a single category of age 90+)

22-432 Effects of narratives on demand for low and high ventilated cigarettes and substitution for alternative products.

	Phone numbers
	Fax numbers
	Electronic mail addresses (e-mail)
	Social Security numbers
	Medical record numbers
	Health plan beneficiary numbers
	Account numbers
	Certificate/license numbers
	Vehicle identifiers and serial numbers, including license plate numbers
	Device identifiers and serial numbers
	Web Universal Resource Locators (URLs)
	Internet protocol (IP) address numbers
	Biometric identifiers, including finger and voice prints (audio recording)
	Full face photographic images and any comparable images (including video recording)
	Student record number or identification number
	User name for online or computer accounts
	Any other unique identifying number, characteristic, or code (note this does not mean the unique code assigned by the investigator to code the data): Click here to explain.

9.0 Sharing of Results with Subjects

9.1 *Describe whether you will share results (study results or individual subject results, such as results of investigational diagnostic tests, genetic tests, or incidental findings) with subjects or others (e.g., the subject's primary care physician). If so, describe how you will share the results and include this information as part of the consent document. Upload materials you will use to explain the results to subjects:*

We will not share study results or individual results directly with the study participants or others.

10.0 Study Timelines

10.1 *Describe:*

- *The duration of an individual subject's participation in the study (for example, 1 hour, 2-4 weeks, 3-5 years).*
- *The amount of time expected to enroll all study subjects (weeks, months, years, etc.)*
- *The amount of time expected for the investigators to complete this study including primary data analyses.*

22-432 Effects of narratives on demand for low and high ventilated cigarettes and substitution for alternative products.

1) Participant's schedule

The participation of one subject is expected to take approximately 2 weeks. Session 1 (Consent and Assessments) is estimated to take approximately 2h. Session 2 (Experimental Tobacco Marketplace) is expected to take approximately 1h30. Session 3 (follow-up) is estimated to take approximately 30 minutes.

*Note that participants will sample/use products between sessions 1 and 3.

2) Study timeline

Enrollment and data collection are expected to take 10 months.

The study team has projected this study to take approximately 1 year to complete enrollment, data collection and data analysis.

11.0 Inclusion and Exclusion Criteria

11.1 Describe how you will screen individuals for eligibility. When will screening occur and what procedures will you use? Upload any screening scripts or surveys to Protocol Management:

We currently use a master screening, which occurs prior to enrolling participants into our research protocols, to effectively decrease attrition in our studies by ensuring that participants meet all inclusion/exclusion criteria prior to enrolling into a study.

11.2 Describe the eligibility criteria that define who will be included and who will be excluded from enrollment for each procedure of your study. Include any geographic criteria (e.g., Virginia Tech undergraduate students, a national sample of adults with engineering degrees, minors aged 8-12 in the New River Valley, university faculty in Virginia and Paris, France):

Inclusion criteria:

- Provide informed consent
- Be at least 21 years of age or older
- Provide a breath sample for measuring carbon monoxide (CO \geq 8 ppm)
- Stable tobacco use patterns for at least three months
- Be willing to sample the study products (high- and low-ventilated cigarettes, and other tobacco products)
- Report smoking a high-ventilated cigarette (16 to 38% ventilation)
- Report smoking at least 10 cigarettes per day

Exclusion criteria:

- Have plans to move out of the area

22-432 Effects of narratives on demand for low and high ventilated cigarettes and substitution for alternative products.

- Have a serious or unstable physical or mental health condition
- Taking a tobacco cessation medication or medication that interferes with nicotine metabolism, motivation or reinforcement
- Report concrete, immediate plans to alter/quit using their usual nicotine products at the beginning of the study

11.3 Indicate specifically whether you will include or exclude each of the following special populations: (You may not include members of these populations as subjects in your research unless you indicate them in the description of your subject population.)

- *Minors, as defined by state law where the study is performed (infants, children, teenagers)*
- *Pregnant women (can be included in minimal risk studies by mentioning in section 13.1)*
- *Prisoners (including all incarcerated individuals)*
- *Adults not capable to consent on their own behalf*

This study will focus on cigarette smokers. We will not include individuals under the age of 21 in compliance with Virginia state law. Minors, pregnant women, prisoners, and adults not capable to consent on their own behalf will be excluded from this study.

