22-432 Effects of narratives on demand for low and high ventilated cigarettes and substitution for alternative products.

potential benefits of quitting and transitioning to less harmful products. The results might inform tobacco control policies.

Study Endpoints

3.4 *Describe the primary and secondary **study** endpoints. See links below for discussion of study endpoints and how they may differ from study objectives. These are most common in clinical trials but are sometimes applicable to other types of biomedical research, as well as social, behavioral, or educational research. See link below for a discussion.*

https://docs.google.com/document/d/1Wocz7K7a0hCQJPPO_khh511SQQjhGDDGHzcOPRHR5Tw/edit?usp=sharing

Substitutability: the two groups will be compared to assess whether substitutability with tobacco products occurs as a function of the intervention and cigarette price.

3.5 *Describe any primary or secondary **safety** endpoints. These should be included for all studies that are greater than minimal risk. (Minimal risk: The probability and magnitude of harm or discomfort anticipated in the research that are not greater in and of themselves than those ordinarily encountered in daily life or during the performance of routine physical or psychological examinations or tests.):*

This study will recruit adults who regularly smoke high-ventilated cigarettes. This study's procedures are not designed to increase daily nicotine use and we do not anticipate any increased risk to participants directly from this study, although there are risks of nicotine use and these are included in the risk section of this protocol and consent.

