6.0 Study Intervention(s)/Investigational Agent(s)

7.1 Describe the study interventions (including behavioral interventions) and/or investigational agents (e.g., drugs or devices) to be used in this study. Consider each of the items listed below:

- *Drug/Device Handling: If the research involves drugs or devices, describe your plans to store, handle, and administer the drugs or devices so that they will be used only on subjects, and only by authorized investigators.*
- *Describe whether any of the following will be used: microwaves, X-rays, DEXA scans, general anesthesia, or sedation*
- *If control of the drugs or devices used in this protocol will be accomplished by following an established, approved organizational SOP (e.g., Research Pharmacy SOP for the Control of Investigational Drugs, etc.), please reference the SOP in this section.*

This study does not involve any smoking cessation interventions. This study does involve experimental manipulation of narratives and of tobacco/nicotine product price to understand consumer's behavior. No drugs or devices will be provided to participants.

6.2 List the name of all drugs (including any vitamins, supplements, herbs, or nicotine) to be used in the study. Indicate whether they have FDA approval, and list any limitations for their use:

The range of products available to sample and purchase includes: cigarettes, chewing tobacco (dip), nicotine gum, nicotine lozenges, e-cigarettes, and snus. All the products that will be available to sample and purchase are FDA approved and available in the real world.

6.3 List all devices, how they will be used, their purpose in the study, and if they will be used in a manner consistent with their approved uses. If they will be used in ways that are not yet FDA approved, indicate whether they

22-432 Effects of narratives on demand for low and high ventilated cigarettes and substitution for alternative products.

need an IDE or a determination that they are exempt from the IDE Determination. If a determination of significant risk or non-significant risk is needed for any of the devices, include the researcher's recommendation for each of those devices:

N/A

6.4 *If the drug is investigational (has an IND) or the device has an IDE or a claim of abbreviated IDE (non-significant risk device), include the following information:*

- *Identify the holder of the IND/IDE/abbreviated IDE.*

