7.0 Procedures Involved

7.1 Describe and explain the study design:

In a between-group within-subject repeated measures design, participants will be randomized to one of three groups (narrative, fact sheet, or control) and complete questionnaires on a computer, sample a range of tobacco products, and complete ETM conditions. Specifically, participants will purchase tobacco products in an online store under five ETM conditions, which include six trials each assessing different cigarette prices: a) high-ventilated cigarette alone, b) low-ventilated cigarette alone, c) high- and low-ventilated cigarette with high-ventilated cigarettes increasing in price, d) high- and low-ventilated cigarette with low-ventilated cigarettes increasing in price, and e) usual, high- and low-ventilated cigarette with usual cigarettes increasing in price.

7.2 *Provide a description of:*

- *All research procedures being performed*
- *If the study has more than one procedure, session, and/or subject population, describe each procedure, session, and/or study population separately. For complex studies, you are encouraged to include a figure or chart.*

Participants will complete 1) an informed consent and assessment session, 2) an ETM session, and a 3) follow-up session. Session 1 and 2 will be separated by an at home sampling phase and Session 2 and 3 will be separated by an at home product use phase.

1) In the consent and initial assessment session, participants will go through standard consent procedures and then provide a breath to confirm recent levels of smoking. Participants will complete a timeline follow back to assess previous month recent smoking, and consumption of nicotine products, and to determine ETM budget. A survey will administer demographics questions and nicotine/tobacco-related assessments (Wisconsin Index of Smoking Dependence Motives, Fagerstrom Test of Cigarette Dependence, Minnesota Nicotine Withdrawal Scale, Perceived Health Risk ratings). At the end of the session, participants will experience a trial of the ETM that will be used in the next session.

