For the sampling phase, participants will be provided two days worth of study cigarettes based on their number of cigarettes smoked per day, half of high-ventilated cigarettes and half of low-ventilated cigarettes. Participants will also be provided with a sample of other commercially available tobacco product to try. Participants will be instructed the order in which to use the products on the next three days. The order will be counterbalanced across participants.

During the sampling phase, participants will receive text messages asking how many of each product they sampled during those days.

2) Before the ETM session, participants will be randomized to the narrative, the fact sheet or the control group. In the ETM session, they will listen to a recording of a narrative of an individual who quit tobacco products or a fact-sheet with overall rates of smoking and its negative consequences. Participants in the control group will not be exposed to any recording. Then, participants will buy tobacco products to use throughout the next 7 days. Participants will complete a total of 30 purchasing trials each for 7 days' worth of products. They will be exposed to 5 conditions with cigarettes increasing in price. A balanced Latin square design will be used to present the following conditions: a) a) high-ventilated cigarette alone, b) low-ventilated cigarette alone, c) high- and low-ventilated cigarettes with high-ventilated cigarettes increasing in price, d) high- and low-ventilated cigarettes with low-ventilated cigarettes increasing in price, and e) usual, high- and low-ventilated cigarettes with usual cigarettes increasing in price. Additionally, participants will complete the Questionnaire on Smoking Urges-Brief, the Product Evaluation Scale, questions about the cigarette harshness, items of the Transport Narrative Questionnaire (narrative and fact sheet groups only), the Positive and Negative Affect Schedule

22-432 Effects of narratives on demand for low and high ventilated cigarettes and substitution for alternative products.

(narrative and fact sheet groups only), a manipulation check and an open-ended question about the recording they listened (narrative and fact sheet groups only), and the Experiment/Experimenter Attitudes Rating Scale.

For the seven days following the ETM session, participants will be asked not to use or purchase any outside tobacco/nicotine products and not to sell or give away any of their purchases.

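### Half of the primary hypothesis concerns how many alternative products are bought, but the models do not adjust for participants' existing use of those products, which Session 1 already records

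*Protocol*

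**What the plan says.** **Eligibility (Protocol 11.2).** The criteria on tobacco use require "Stable tobacco use patterns for at least three months" and "Report smoking at least 10 cigarettes per day". The exclusions cover people "Taking a tobacco cessation medication or medication that interferes with nicotine metabolism, motivation or reinforcement" and those who "Report concrete, immediate plans to alter/quit using their usual nicotine products at the beginning of the study". None bars or limits current use of e-cigarettes, snus or dip. The last exclusion concerns planned change, and its plural wording is compatible with people who use several products.

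**Marketplace (Protocol 6.2).** The products on sale are "cigarettes, chewing tobacco (dip), nicotine gum, nicotine lozenges, e-cigarettes, and snus".

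**Baseline data (Protocol 7.2, Session 1).** A timeline follow-back covers the previous month's smoking and "consumption of nicotine products, and to determine ETM budget". Setting the budget is its only stated use beyond description.

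**Allocation (Protocol 7.2, Session 2).** "Before the ETM session, participants will be randomized to the narrative, the fact sheet or the control group". No ratio, blocking or stratification factor is stated.

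**Outcome.** The hypothesis in Protocol 2.2 is about purchases: fewer ventilated cigarettes and more alternative products. The endpoint in Protocol 3.4 is to "assess whether substitutability with tobacco products occurs as a function of the intervention and cigarette price", with no formula.

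**Analysis (Protocol 4.2 and the SAP, same text).** A within-between ANOVA with group, condition, their interaction and order effects, followed by post-hoc contrasts between groups. No baseline covariate is named. Both documents add only that further analyses are possible.

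**The concern.** Someone who already vapes or uses snus is likely to buy those products in the marketplace whichever recording they hear. Their purchases add to the spread of the alternative-product outcome. If such people fall unevenly across three groups of about 30, the unevenness moves the group means. The plan collects the variable that would account for this and then does not use it in the analysis.

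At stake are the precision of the between-group contrasts on alternative-product purchases, and how readily a difference could be attributed to the message when the groups happen to differ in existing use.

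**Working it through.** **1. The plan's own sample size.** Protocol 13.1 gives three groups, two measurements, f = 0.25, alpha = 0.01 and 95% power. The correlation between measurements is not stated; 0.5 is assumed here. For the within-between interaction:

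- lambda = f² × N × m / (1 − rho) = 0.0625 × N × 2 / 0.5 = 0.25N
- df = 2 and N − 3
- Power is 0.952 at N = 88 and 0.957 at N = 90.

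Rounding 88 up to a multiple of three gives the stated 90, and 90 / 0.9 = 100 enrolled. The figure reproduces, and nothing below changes it.

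**2. Assumed inputs (none in the documents).**

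- Equal allocation: 90 / 3 = 30 per group.
- Share of existing users of alternative products: p = 0.2 to 0.4.
- Existing users' excess in alternative purchases: D = 0.5 to 1.0 SD, where the SD is taken among people of the same use status.
- Outcome: one purchase-level value per person.

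**3. Chance imbalance between two given groups.** SD of the difference in shares = sqrt(2p(1 − p)/30). The probability of a gap of five or more people (5/30 = 17 points) is exact binomial.

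| p | SD of difference | P(gap of 5 or more) |
|---|---|---|
| 0.2 | 0.103 | 0.145 |
| 0.3 | 0.118 | 0.204 |
| 0.4 | 0.126 | 0.235 |

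For a gap of that size between some pair among the three groups, simulation (400,000 draws) gives about 31%, 41% and 46%.

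**4. What existing use explains, and what adjustment gains.** Let v = p(1 − p)D². Variance explained is R² = v/(1 + v). Without adjustment, the standard error of a 30 v 30 contrast is sqrt(2/30) = 0.258 total SD. With adjustment it is 0.258 × sqrt(1 − R²). The shift from a five-person gap, in the same total SD units, is (5/30) × D / sqrt(1 + v).

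| p | D | v | R² | Adjusted SE | Cut in SE | Shift | Shift / 0.258 |
|---|---|---|---|---|---|---|---|
| 0.2 | 0.5 | 0.04 | 0.038 | 0.253 | 2% | 0.082 | 0.32 |
| 0.4 | 0.5 | 0.06 | 0.057 | 0.251 | 3% | 0.081 | 0.31 |
| 0.2 | 1.0 | 0.16 | 0.138 | 0.240 | 7% | 0.155 | 0.60 |
| 0.4 | 1.0 | 0.24 | 0.194 | 0.232 | 10% | 0.150 | 0.58 |

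**5. Effect on the error rate.** By normal approximation at two-sided alpha 0.01, the type I error given a five-person gap is about 0.011 to 0.017 over these four settings. Averaged over all randomisations it stays nominal.

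**6. Which outcomes are affected.** Protocol 3.1 treats substitution as a rise in use of a fixed-price product while another product's price increases. A person who buys the same extra amount c at every price adds c to each point and nothing to the slope. An amount that is the same in every condition cancels from differences between conditions, and so from the group-by-condition interaction. It remains in purchase level, and therefore in the between-group contrasts on level. Slopes and the interaction are affected only if existing users also respond differently to price or condition.

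**The case against.** The strongest reply is that this describes any prognostic variable in any unstratified trial. Randomisation makes existing use independent of group in expectation, and the test's error rate already allows for chance imbalance. That stands. A five-person gap moves a contrast by only 0.3 to 0.6 of a standard error.

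The second reply is that substitution, as the protocol defines it, is a slope, from which a steady habit drops out. That also stands, and it confines the point to purchase levels. It does not remove the point, because Protocol 2.2 states the hypothesis in terms of purchases, the endpoint has no formula limiting it to slopes, and between-group contrasts are planned.

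Three stronger readings are tempting and not supported:

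- **That dual use biases the trial or contaminates substitution as such.** Steps 5 and 6 show that it does not.
- **That eligibility is inconsistent because it bars cessation medication but admits vapers.** Protocol 11.2 does not say whether gum or lozenges count as cessation medication, so the contradiction cannot be established; this is missing detail. Selecting smokers who are not trying to change while admitting stable users of several products is coherent, and fits the aim in Protocol 3.1 of conditions like most smokers' lives.
- **That allocation ignores baseline use.** The protocol does not describe the allocation method, so this would be an inference from silence.

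**Conclusion.** The point holds as a low-cost improvement in precision, not as a threat to validity. The documents establish that current users of e-cigarettes, snus and dip may enter, that their use is recorded in Session 1, that purchases of those products are part of the primary hypothesis, and that no baseline covariate is specified.

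Under the assumed ranges the gain is a 2-10% smaller standard error for between-group contrasts on purchase level, with correction of chance shifts of about 0.08-0.15 SD when two groups differ by five people. The size depends entirely on the assumed share of existing users, their excess purchases and equal allocation. If few entrants use other products, or use predicts purchases weakly, the gain is close to nil.

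**What to change.** In Protocol 4.2 and the SAP, state that models for alternative-product purchases include past-month use of the marketplace's non-cigarette products (any versus none, from the Session 1 timeline follow-back) as a prespecified baseline covariate.

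The cost is one sentence and 1 df. No new data are needed and N stays at 90. The value describes the month before Session 1 and the recordings are heard only in Session 2, so the intervention cannot affect it.

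Stratifying the randomisation by the same variable is optional. It balances the groups, but the model term is what removes the variance, so the covariate alone gives most of the benefit and leaves the allocation list untouched. No change to eligibility is needed for this point.
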